4.3 Study Enrollment Procedures

Outpatient subjects will be recruited from patients seen in the UNC Respiratory Diagnostic Center (RDC) who have tested positive for SARS-CoV-2+ and consented to be contacted for participation in COVID-related research studies. The potential subjects will have signed a prior facility consent at the RDC confirming their willingness to share their name and contact information to be contacted for study participation in COVID-19 related research. We will not receive information on subjects that decline this internal consent. A brief review of the patient's Epic chart will take place for medical screening and to identify any missing contact information, as needed. Subjects will be contacted for recruitment by phone and (if unreachable by phone) by secure email by study personnel; patients will have the study rationale and risks explained and will be provided time to ask questions and consider participation. If patients are interested in participating, both appointments will be scheduled for them at the Adams School of Dentistry Go Health Clinical research core. Consent documentation will be signed in person and in private in the Go Health Clinical Research Core.

For Spanish speaking patients and/or parents, Spanish forms will be provided and communication will occur through a Spanish translator. All patients are adults and over normal cognitive capacity, and therefore will be able to consent for themselves. A list of SARS-CoV-2+ subjects that have consented to be contacted for research, will be provided by the RDC clinic, sent via secure UNC servers or secure UNC email to our research team's clinical coordinator, and this list will include names and contact details (PHI). This list is updated daily and provided to approved research sites, including ours.

At the visit, a consented patient will answer screening questions regarding inclusion and exclusion criteria. Answers will be entered into the CDART research database managed by UNC. Prior to finalizing these screening questions, women participants of childbearing potential will be asked to provide a urine sample in the restroom, to undergo a rapid pregnancy test by study personnel. Any pregnant or lactating patients will be excluded.

All of the consenting eligible patients will be enrolled in the study and will then be allocated to the treatment regimens by randomization. A statistician will create a block randomization schedule and perform these computations. All patients will be consented and then fill out our screening questions for inclusion and exclusion to confirm eligibility prior to being assigned to the randomization schedule.

5. STUDY INTERVENTIONS

5.1 Interventions, Administration, and Duration

Patients who meet all inclusion criteria without any exclusions will be asked to give a baseline salivary sample of 2 mL over 5 min. The patient will then be asked to rinse with an unlabeled/blinded antiseptic mouth rinse for 60 sec. Once the participant expectorates the mouth rinse, a time 0, 2 mL salivary sample will be collected over 5 min. During the 10 min recuperation period post rinse, the participant will answer survey questions about their demographics and regarding the taste, color, flavor and acceptability of using the mouth rinse as part of routine dental and medical visits. At 15 min post-rinse, the patient will be asked to provide an additional 2 mL saliva sample over the course of 5 min, followed by another 10 min break. This sequence repeats for

the 30, 45 and 60-min time points. At 60 min, the patient will give a final 2 mL salivary sample. Peripheral blood will be collected at the end of salivary collection (2 - 5 mL in EDTA-containing blood collection tubes).

Participants will be provided materials and oral hygiene instruction related to daily use of oral hygiene products provided by study sponsors. In the one week between study visits, participants will be directed to brush with Colgate toothpaste (at least twice per day) and rinse with the Colgate mouthrinse (2-3 times per day based on-label directions). Participants will be asked to keep a daily diary of oral hygiene performance, product usage, COVID symptoms and exposures. Study personnel will monitor daily diary adherence and will reach out to participants between visits 1 and 2 to ensure home oral hygiene protocol adherence by phone or email. Participants will be given a \$30 gift card for their participation in visit 1.

Participants will be scheduled to return to the GoHealth Clinical Research Unit at one week after the baseline assessment, during which additional salivary (1 time point, 2 mL of saliva over 5 min, no rinse will occur) and blood samples will be collected. At the conclusion of sample collection, the participant will undergo a periodontal exam and will receive a \$50 gift card for their participation in visit 2. Once collected, the periodontal exam data will be evaluated and the periodontal status for each participant will be assigned via the case definitions for periodontitis, gingivitis, and clinical periodontal health as described in the 2017 World Workshop on the Classification of Periodontal and Peri-Implant Diseases and Conditions and the 2012 Centers for Disease Control and Prevention and American Academy of Periodontology case definitions.^{19, 20} Patients will be informed of their periodontal status. Patients with any periodontitis or gingivitis diagnosis will be informed of their diagnosis at the time of the visit and will be referred to an oral healthcare provider for further treatment. This study involves two on-site 90 minute visits. Study participation concludes at the end of the second on site visit with no additional follow-up, as results are not relevant to the patient's clinical course and treatment management.

5.2 Handling of Study Interventions

Mouthrinses will be acquired from the following sources:

mouthrinse*	Source: Colgate company providing their commercially available, commercially packaged and ready-for-sale products
1.5% w/v Hydrogen Peroxide rinse	Peroxyl- Colgate
0.12% Chlorhexidine Gluconate	Periogard- Colgate
0.075% Cetylpyridinium Chloride	Colgate Total Zero- Colgate

Sterile water	CVS store
---------------	-----------

**All mouthrinses are commercially available in the USA, routinely used in clinical settings, and will be used in an on-label manner.*

Mouthrinses will be prepared by research study staff in a 50 mL sterile conical tube. The conical tube will be unlabeled so both the participant and study personnel will be blinded to the solution. Any adverse events or protocol deviations will be reported to the UNC IRB. Weekly meetings of the internal quality control committee will allow us to closely monitor such events.

5.3 Concomitant Interventions

There are no concomitant interventions other than the mouthrinse and a short survey.

5.3.1 Allowed Interventions

There are no additional interventions, other than mouth rinsing with one of the mouthrinse options and using commercially available Colgate toothpaste and mouthrinse at home, as previously described. If patients have an allergic reaction, EMS will be contacted for management, and therefore no rescue medications are indicated.

5.3.2 Required Interventions

The patient will rinse with a blinded mouthrinse for 30-60 seconds (as specified on the label) and then will spit it out, followed by donating saliva and blood samples.

5.3.3 Prohibited Interventions

Patients who have brushed their teeth, drank or eaten within an hour of the study visit will be directed to wait until an hour has elapsed; if they cannot wait, the patient will be excluded. Patients who have used a mouthrinse within 48 hours of the study will be excluded.

Patients who have participated in a study of other oral products (toothpaste, mouthrinses) within the prior 30 days will be excluded.

Patients who are currently abusers of alcohol or recreational drugs, and have used such products within 48 hours will be excluded

5.4 Adherence Assessment

Adherence would be defined as rinsing with the mouthrinse for 30-60 sec (as directed on the label) before expectorating, and then providing saliva samples at 15 min time points and a blood sample.

6. STUDY PROCEDURES

6.1 Schedule of Evaluations

Assessment	Screening: Visit-1 (Day-14 to Day -1)	Baseline, Enrollment, Randomization, Intervention: Visit 1 (Day 0)	Visit 2
Informed Consent Form	X	X	
Demographics	X	X	
Medical History	X	X	X
Current Medications	X	X	X
Blood Chemistries		X	X
Urine Analysis- pregnancy		X	
Vital Signs		X	X
Brief Oral Exam	X	X	
Periodontal Exam			X
Inclusion/Exclusion Criteria	X	X	
Enrollment/Randomization	X	X	
Treatment Admin. Form		X	
Concomitant Medications	X	X	X
Adverse Events	X	X	X

6.2 Description of Evaluations

Subjects are required to be onsite for two 90-minute appointments. Subjects will be asked to rinse with an unlabeled/blinded antiviral mouth rinse for 30-60 sec and provide 2 mL of saliva prior to the rinse and 2 mL of saliva immediately post-rinse, 15 min post-rinse, 30 min post-rinse, 45 min post-rinse, and 60 min post-rinse. Subjects will also be asked to complete a short survey about the rinsing experience. A blood sample will also be collected, and a brief oral exam will occur. At the end visit, a single saliva sample and blood sample will be taken, along with a periodontal exam.

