Samples will be evaluated at both timepoints for inflammation-related cytokines and chemokines using pre validated quantitative multiplex assays (Luminex technologies), diaries will be reviewed and periodontal charting will be evaluated for differences between patient groups. A periodontal exam will consist of periodontal probing depths (PD), clinical attachment level (CAL) and bleeding on probing (BOP) at six sites for each tooth excluding third molars. Once collected, the periodontal exam data will be evaluated and the periodontal status for each participant will be assigned via the case definitions for periodontitis, gingivitis, and clinical periodontal health as described in the 2017 World Workshop on the Classification of Periodontal and Peri-Implant Diseases and Conditions and the 2012 Centers for Disease Control and Prevention and American Academy of Periodontology case definitions.^{19,20} Patients will be informed of their periodontal status. Patients with any periodontitis or gingivitis diagnosis will be informed of their diagnosis and will be

referred to an oral healthcare provider for further treatment. Patients' final periodontal status will be the tertiary outcome of the periodontal exam and will be reported as the percentage of participants categorized into each diagnostic group. This study involves two on-site 90-minute visits.

Known and potential risks include breach of confidentiality, slight discomfort, and a low chance of a previously undiagnosed allergy. To minimize risk of breach of confidentiality, all patients will be assigned a unique study ID. There will be no other subject identifiers on samples or data. The linkage file that relates patient's names to study ID numbers will be stored on a UNC secure server. All desktops computers and servers are kept in locked facilities and in accordance with UNC IT/security safeguards and policies.

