All providers and study researchers have been trained in and abide by HIPAA procedures, and confidential patient information will be stored on secured, encrypted UNC servers. Patients will already have been provided with their SARS-CoV-2 status through their healthcare providers, and this confidential medical information will not be released by any study personnel. Some patients may perceive the mouth rinse as causing some discomfort if they dislike the flavor or the bubbling sensation. A small fraction of patients (rare <1%) may be allergic to the mouth rinse. We will ask detailed questions in our screening protocol if patients are allergic to any component of the mouthrinses, but if a patient answers no to all screening questions regarding allergy and then they are allergic, it may lead to an adverse allergic reaction.

The following table lists adverse effects associated with each mouthrinse proposed in this study:

mouthrinse*	Adverse effects
1.5% w/v hydrogen peroxide rinse (Peroxyl)	
• If irritation persists for 7 days, is severe, is due to orthodontic appliances and/or dentures, or swelling or fever develops, the patient's condition needs to be re-evaluated by a doctor or dentist.• Overdose can injure the gums and continued use of hydrogen peroxide may cause reversible hypertrophy of the papillae of the tongue known as 'black hairy tongue' therefore using this product at high doses or for long periods of time is not recommended.• Some cases of mucosal irritation and swelling of the oral tissues have been reported specially with high doses or in continued use.

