0.12% Chlorhexidine Gluconate (Periogard)	
• The most common (1) an increase in staining of teeth and other oral surfaces, (2) an increase in calculus formation, and (3) an alteration in taste perception; see WARNINGS and PRECAUTIONS. Oral irritation and local allergy-type symptoms have been spontaneously reported as side effects associated with use of chlorhexidine gluconate rinse. The following oral mucosal side effects were reported during placebo-controlled adult clinical trials: aphthous ulcer, grossly obvious gingivitis, trauma, ulceration, erythema, desquamation, coated tongue, keratinization, geographic tongue, mucocoele, and short frenum. Each occurred at a frequency of less than 1.0%. Among postmarketing reports, the most frequently reported oral mucosal symptoms associated with chlorhexidine gluconate oral rinse are stomatitis, gingivitis, glossitis, ulcer, dry mouth, hypesthesia, glossal edema, and paresthesia. Minor irritation and superficial desquamation of the oral mucosa have been noted in patients using chlorhexidine gluconate oral rinses. There have been cases of parotid gland swelling and inflammation of the salivary glands (sialadenitis) reported in patients using chlorhexidine gluconate oral rinse.

1:1.5% w/v hydrogen peroxide rinse (Peroxyl) 2 nd : 0.12% Chlorhexidine Gluconate (Periogard)	
 • No additional adverse effects documented from sequential use. • Please see above for adverse effects of each rinse individually. • For the sequential Peroxyl (1st) and Periogard (2nd) rinses, both oral rinses will be conducted in an on label fashion. The patient will begin by rinsing with 10 mL of Peroxyl for 60 seconds and then expectorate the mouthrinse into an empty tube. Then the patient will rinse with 15 mL of Periogard for 30 seconds, and spit this mouthrinse into a separate tube.
0.075% Cetylpyridinium Chloride (Colgate Total Zero)	
 • If more than used for rinsing is accidentally swallowed, get medical help or contact a Poison Control Center right away
Sterile Water	No contraindications

**All mouthrinses are commercially available in the USA, routinely used in clinical settings, and will be used in an on-label manner.*

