6.2.1 Screening Evaluation

Consenting Procedure: Patients will be contacted first by phone and, if not available, then by email. The consent process will be conducted by trained study coordinators. The study's purpose and requirements will be explained and the patient will have the opportunity to ask questions and will have time to consider participation. Interested patients will make an appointment to visit the Go Health Clinical Research Unit at Adams School of Dentistry for this study. Study participation. The consent forms will be reviewed and signed by interested patients in person in the Go Health Clinical Research Unit at Adams School of Dentistry prior to study participation. For Spanish speaking patients and/or parents, Spanish forms will be provided and communication will occur through a Spanish translator. All patients are adults and over normal cognitive capacity, and therefore will be able to consent for themselves.

Screening

- At the visit, a consented patient will answer screening questions regarding inclusion and exclusion criteria. Answers will be entered into the CDART research database managed by UNC. A brief oral exam will take place to evaluate for existing severe oral trauma, severe periodontal disease, tumors or infection.
- Prior to finalizing these screening questions, women participants of childbearing potential will be asked to provide a urine sample in the restroom, to undergo a rapid pregnancy test by study personnel. Any pregnant or lactating patients will be excluded.

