6.2.2 Enrollment, Baseline, and/or Randomization

Enrollment

Outpatient subjects will be recruited from patients seen in the UNC RDC who have tested positive for SARS-CoV-2+ and consented to be contacted for participation in COVID-19-related research studies. The subjects being approached by phone or email have signed a prior facility consent at the RDC confirming their willingness to share their name and contact information to be contacted for study participation in COVID-19-related research. We will not receive information on subjects that decline this internal consent. A brief review of the patient's Epic chart will take place for medical screening and to identify any missing contact information, as needed. Subjects will be contacted for recruitment by phone and (if unreachable by phone) by secure email by study personnel; patients will have the study rationale and risks explained and will be provided time to ask questions and consider participation.

If patients are interested in participating, appointments will be scheduled for them at the Adams School of Dentistry Go Health Clinical research core. Subjects must be able to attend both visits, to be enrolled. Consent documentation will be signed in person and in private in the Go Health Clinical Research Core. A list of SARS-CoV-2+ subjects that have consented to be contacted for research, will be provided by the RDC clinic, sent via secure UNC servers or secure

UNC email to our research team's clinical coordinator, and this list will include names and contact details (PHI). This list is updated daily and provided to approved research sites, including ours.

Baseline Assessments

In this application, "baseline" refers to the initial saliva sample taken before the participant uses a mouthwash." For this baseline saliva sample, we will measure the salivary viral load and infectivity. The initial brief oral exam will also be a baseline visual inspection.

Randomization

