8.3 Adverse Events and Serious Adverse Events

An **adverse event (AE)** is generally defined as any unfavorable and unintended diagnosis, symptom, sign (including an abnormal laboratory finding), syndrome or disease which either occurs during the study, having been absent at baseline, or if present at baseline, appears to worsen. Adverse events are to be recorded regardless of their relationship to the study intervention.

A **serious adverse event (SAE)** is generally defined as any untoward medical occurrence that results in death, is life threatening, requires inpatient hospitalization or prolongation of existing hospitalization, results in persistent or significant disability/incapacity, or is a congenital anomaly.

The use of on-label, widely used mouthrinses and toothpastes and collection of saliva and blood carry minimal risk for participants, apart from the very rare, undiagnosed allergy, or the unlikely event that a participant slips or falls during the study, which would be managed through proper referral to the neighboring UNC hospital.

The investigator and team will meet weekly to review safety concerns, unanticipated problems or adverse events. All adverse events will be reported to the IRB and the committee overseeing the study within 30 days.

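### No structured inspection of the tongue, non-gingival mucosa or salivary glands is planned after the week of home rinsing, although the protocol lists harms at those sites

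*Combined protocol and SAP*

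**What the plan says.** In section 6.1, the row "Brief Oral Exam" is marked at screening and visit 1 and is blank at visit 2. Section 6.2.1 gives the purpose of that exam: "A brief oral exam will take place to evaluate for existing severe oral trauma, severe periodontal disease, tumors or infection". Section 6.2.2 adds: "The initial brief oral exam will also be a baseline visual inspection".

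For visit 2, section 6.2 states: "At the end visit, a single saliva sample and blood sample will be taken, along with a periodontal exam". The other descriptions of visit 2 (Précis, sections 2.2, 3, 5.1 and 6.2.5) agree. Section 6.1 also marks medical history, vital signs and adverse events at visit 2.

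The adverse effect tables in sections 2.2 and 8 list harms by rinse. For the peroxide rinse: "Some cases of mucosal irritation and swelling of the oral tissues have been reported specially with high doses or in continued use"; overgrowth of the tongue papillae is listed as well. For chlorhexidine: "Minor irritation and superficial desquamation of the oral mucosa have been noted in patients using chlorhexidine gluconate oral rinses"; ulcer, glossitis, parotid swelling and sialadenitis are among the other entries.

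Under section 8.3 an adverse event includes a sign or symptom "which either occurs during the study, having been absent at baseline, or if present at baseline, appears to worsen".

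**The concern.** The harms that the protocol names for its rinses lie largely on the tongue, the general oral mucosa and the salivary glands. For the peroxide rinse the protocol links them to high doses or to continued or prolonged use, and continued use happens at home, between the visits. The general look at the mouth comes before that week, and the examination after it is confined to teeth and gingiva.

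The adverse event definition depends on whether a sign is new or worse than at baseline. A baseline inspection without a matching later one does not serve that comparison.

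What is at stake is the completeness of the safety record by arm, and the sensitivity of the safety review in section 10.4, which is triggered by the number of events observed. The efficacy analysis is not involved.

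**Working it through.** The plan states no figure on this point, so the check is mainly a comparison of sections.

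**1. What is examined, and when**

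| Site | Before or at visit 1 | Visit 2 |
|---|---|---|
| Gingiva and teeth | Brief oral exam (severe disease only) | Plaque index, gingival index, probing depth, attachment level, bleeding (sections 7.0 to 7.5) |
| Tongue, other mucosa | Brief oral exam; sites not named in 6.2.1 | No defined item |
| Salivary glands | Not named | No defined item |
| Anything reported | Adverse events, medical history | Adverse events, medical history |

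The gingival index (7.1) does record redness, edema and ulceration, and the plaque index (7.2) includes extrinsic stain. Both are scored only at visit 2, so such findings have no scored baseline for section 8.3.

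**2. Which arms are affected**

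Harms at the uninspected sites are listed for the peroxide and chlorhexidine rinses. Three of the four antiseptic arms contain one or both, which is 3 × 30 = 90 enrolled or 3 × 25 = 75 with full data. The cetylpyridinium entry mentions only swallowing. The Précis says that controls receive no Colgate products for home use.

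**3. Share of exposure after the last scheduled brief oral exam**

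Inputs: seven days between visits (Précis), two to three home rinses a day (section 3), and one supervised occasion at visit 1. The sequential regimen is counted as one occasion.

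- Lower: 7 × 2 = 14 home occasions; 14 / (14 + 1) = 93%.
- Upper: 7 × 3 = 21 home occasions; 21 / (21 + 1) = 95%.

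This is a share of exposure. It is not a share of harms missed.

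**4. Other routes of detection**

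- The diary (section 3) covers hygiene, product use, COVID-19 symptoms and exposures. No oral side-effect item is named.
- Contact between visits (section 5.1) is for adherence.
- The acceptability survey is answered during the pause after the visit 1 rinse.
- The follow-up call in section 8.5 is made after an event is already known.
- What remains is the visit 2 adverse event and medical history collection. Section 8 does not say how that information is elicited.

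**5. Illustration of the safety review**

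Section 10.4 triggers a review at more than 1 event per 20 patients and does not say whether this is counted by arm. Read by arm, with 30 enrolled, more than 1.5 means at least 2. With true event rate p and share recorded s, set q = p × s. Then

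P(review) = 1 − (1 − q)^30 − 30q(1 − q)^29.

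The documents give neither p nor s, so the values below are assumptions.

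| True rate p | s = 100% | 75% | 50% | 25% |
|---|---|---|---|---|
| 10%, n = 30 | 0.82 | 0.67 | 0.45 | 0.17 |
| 5%, n = 30 | 0.45 | 0.31 | 0.17 | 0.05 |
| 10%, n = 25 | 0.73 | 0.57 | 0.36 | 0.13 |

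The direction does not depend on these choices, because fewer recorded events always make the review less likely.

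**The case against.** A reader might infer that the listed harms are never looked for after home use, or that only what a participant volunteers could reveal them. The documents do not support either reading. Adverse events and medical history are scheduled at visit 2, section 8.3 covers signs as well as symptoms, and nothing says that collection is passive. Nor are the only oral inspections before exposure. At visit 2 a trained and calibrated examiner goes round the whole mouth, scores gingival ulceration and stain, and is free to report a lesion seen elsewhere. This objection stands, and it limits the point to the lack of a structured inspection of particular sites.

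The stated purpose of the first exam is mainly an eligibility screen, and a screen needs no later counterpart. That is fair. The word baseline in section 6.2.2 is thin evidence that a comparison was intended.

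The listed harms may also be rare here. Home use is one week and on-label, while the tables link the tongue effect to high doses or long use. The mucosal effects from the placebo-controlled chlorhexidine trials each occurred at under 1.0%. Over two chlorhexidine arms that is fewer than 50 × 0.01 = 0.5 cases among completers, or 60 × 0.01 = 0.6 among those enrolled, per listed effect. This keeps the severity low. It does not close the gap: the bound applies to each effect singly, and no rate is given for the postmarketing effects, the salivary gland effects or the peroxide effects.

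Finally, section 10.4 speaks of events or reactions witnessed, which can include reported ones, so the review does not depend on visual inspection alone. Subjective signs tabulated by arm could also carry assessment bias, because section 6.2.3 does not name the periodontal examiner among those blinded. Both points are right, and the second is dealt with in the fix.

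**Conclusion.** The gap is real but narrow. After home use, no defined procedure inspects the tongue, the non-gingival mucosa or the salivary glands. Harms that the protocol lists at those sites would be found only through general adverse event and medical history collection or by chance at the periodontal exam. Between 93% and 95% of rinse occasions in the antiseptic arms fall in that period, assuming seven days of home use as directed.

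Less noticeable signs may therefore be under-recorded, and the section 10.4 review may be less sensitive than intended. The number of signs missed cannot be derived from the documents, and the review probabilities above illustrate direction only. Severity is low: this is a cheap improvement to safety ascertainment, with no effect on the primary endpoint.

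**What to change.** - In sections 6.1 and 6.2, mark the brief oral exam at visit 2 as well, done by the periodontal examiner before that examiner learns the participant's arm.
- Use one short form, identical at visits 1 and 2 and in all five arms, that names mucosa, tongue and salivary glands.
- Record any sign that is new or worse than at visit 1 as an adverse event under section 8.3, and tabulate these by arm.
- Sections 6.2.5 and 9 make the visit 2 payment depend on undergoing an oral exam. This probably means the periodontal exam, but it should be reconciled with the blank visit 2 cell in section 6.1.

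The cost is a minute or two of chair time, a slightly wider visit 1 exam, a short new form (the CDART forms listed in section 11.2 include none for an oral exam), and probably a few more minor adverse events to report. No extra visit, staff or invasive procedure is needed.
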